4.3.4 Analysis software

All statistical tests and graphs will be performed using Microsoft excel, and SPSS for Windows version 22 (SPSS IBM Corp. Ltd. Armonk, NY).

4.4 SAFETY REPORTING

All safety reporting will be performed on the ITT population as per CTCAEv5.0 guidelines.

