3.5.3 Details of guidelines for stopping the trial early: Nil

3.5.4 Statistical analysis:

Continuous variables will be expressed as mean (SD) or median (range) and compared by Student's t-test or Mann-Whitney U test as appropriate. The categorical data will be analyzed using Chi-Square or Fisher's exact test. To compare pre and post values, a paired t-test or Wilcoxon signed-rank test will be used. To find out the predictor in survival analysis Cox-proportional hazard regression analysis will be applied. The actuarial probability of survival will be calculated by the Kaplan-Meier graph and compared by the log-rank test. The p value < 0.05 will be considered statistically significant.

3.5.5 Timing of final analysis: The final trial analysis will be performed once the trial is completed or the recruitment of patients ends or at the end of follow up (probably Jan 2021)

3.5.6 Timing of outcome assessments: Jan 2021.

Section 4: Statistical Principals:

4.1 Confidence intervals and P-values: The p value < 0.05 will be considered statistically significant.

Description and rationale for any adjustment for multiplicity:

No adjustments to the type I error will be made as there will be two groups.

Confidence intervals to be reported: Will be reported at 95%.

4.2 Adherence and Protocol deviations: No protocol deviation is expected and will adhere to the defined protocol of trial.

4.3 Analysis populations:

4.3.1 Definition of analysis populations:

Intention-to-treat (ITT) analysis of the sample/population of interest will be carried out in the severe COVID-19 infected individuals. There is no plan to do per-protocol (PP) population analysis as none will be allowed to switch to other treatment group.

4.3.2 ITT population:

This population includes all patients that will be randomized regardless of treatment adherence.

All summaries and analysis will be on the ITT population unless otherwise specified.

4.3.3 PP population:

Not applicable.

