4.4.1 Serious adverse events

Serious Adverse Event (SAE) or Serious Adverse Reaction (SAR): any untoward medical

Occurrence or effect that at any dose of plasma transfusion:

- Results in death
 - Is life threatening
- refers to an event in which the patient will be at risk of death at the time of the event; it does not refer to an event which hypothetically might have caused death if it is more severe
- Requires hospitalization, or prolongation of existing in patients 'hospitalization
 - Results in persistent or significant disability or incapacity
 - Is a congenital anomaly or birth defect?

Medical judgment should be exercised in deciding whether an AE/AR is serious in other situations. Important AE/ARs that are not immediately life-threatening or do not result in death or hospitalization but may jeopardize the patient or may require intervention to prevent one of the other end points listed in the definition above, should also be considered serious. Information regarding serious toxicity, including Principal Investigator (PI) assessment, CTCAEv5.0 grade, will be summarized. Frequencies of all CTCAE events reported as SAEs will be produced and sorted by total frequency (high to low) and categorized using CTCAE system.

Section 5: Trial Population:

5.1 Screening data: All cases with possible COVID-19 will be screened for possible inclusion into the study based on inclusion and exclusion criteria.

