5.3 Recruitment: Consort flow will include as per protocol-

Patients will be assessed for eligibility >>>randomization will be done for eligible participants >>> Allocation of treatment in two groups (one arm will be given convalescent plasma with standard medical treatment and another arm will be given standard medical treatment only) >>> follow up till 28 days.

5.4 Withdrawal/ Follow-up: Withdrawal is not expected, follow up till 28 days in all enrolled patient.

5.5 Baseline patient characteristics: following variables will be considered:

- Age at screening (years) = date of screening.
- Time from initial admission to randomization(days) = date of transfusion allotment by snooze method and transfusion of plasma.
- O₂ saturation at baseline.
- PiO₂/FiO₂ ratio at baseline.
- Respiratory rate at baseline.
- Need of Mechanical ventilation at baseline.
- SOFA score at baseline.
- For those who died: Date of death – transfusion start date or date of randomization.
- For those who are alive: Date of last follow-up – transfusion start date or date of randomization.

Section 6:

Analysis

6.1 Outcome definitions:

6.1.1 Definition of primary endpoint: Time to clinical improvement (Clinical improvement: Reduction of two points in ordinal scale or live discharge from the intensive care unit, whichever is earlier)

6.1.2 Secondary endpoints:

1. The proportion of patients in each category according to the ordinal scale at 48 hours and day 7, 14, and 28 after randomization
2. Duration of oxygen therapy
3. Duration of hospital stay
4. The proportion of patients on mechanical ventilation at day 7. (after randomization)
5. Mortality at day 7 and day 28 (after randomization)
6. Duration of Intensive Care Unit stay
7. Incidence of adverse effects in both groups
8. Presence of antibodies against SARS-CoV-2 in serum after plasma administration.
9. Cytokines and acute phase reactants

6.2 Analysis methods:

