Continuous variables will be expressed as mean (SD) or median (range) and compared by Student's t-test or Mann-Whitney U test as appropriate. The categorical data will be analyzed using Chi-Square or Fisher's exact test. To compare pre and post values, a paired t-test or Wilcoxon signed-rank test will be used. To find out the predictor in survival analysis Cox-proportional hazard regression analysis will be applied. The actuarial probability of survival will be calculated by the Kaplan-Meier graph and compared by the log-rank test. The p value < 0.05 will be considered statistically significant.

6.3 Missing data: Not expected, if data are, we will try to impute.

6.4 Additional analyses: Not planned, if required an appropriate analysis will be carried out.

6.5 Harms: The risks will be the same as the risks related to the transfusion of Plasma Components, which are described below in the table. No additional risks of transfusing Convalescent plasma (CP) therapy are expected as a part of enrolment in this study as per previous literature available. The patient will be managed according to the standard of care at treatment centre. All the adverse transfusion events will be recorded and managed by clinicians or investigators as per standard treatment. Risk of Transfusion transmitted Infections (TTI) like transmission of HIV, Hepatitis B and Hepatitis C, Syphilis, and Malaria are very rare due to standard TTI testing of plasma donors at ILBS, New Delhi as per Drug and Cosmetics Act and Rules.

6.6 Statistical software: All statistical tests will be performed using SPSS for Windows version 22 (SPSS IBM Corp. Ltd. Armonk, NY).

6.7 Important references:

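### Transfusion reactions are to be reported over all patients randomised to plasma; if some are never transfused, the rate comes out too low by exactly that share (minor, cheap to mend)

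*SAP*

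**What the plan says.** - Safety population, SAP 4.4: "All safety reporting will be performed on the ITT population as per CTCAEv5.0 guidelines".
- ITT population, SAP 4.3.2: "This population includes all patients that will be randomized regardless of treatment adherence". The same section makes it the default: "All summaries and analysis will be on the ITT population unless otherwise specified". Nothing in the safety or harms sections specifies otherwise, and no safety or as-treated set is defined.
- Definition of a serious event, SAP 4.4.1: it is tied to exposure, as an untoward "Occurrence or effect that at any dose of plasma transfusion".
- Harms, SAP 6.5: the risks are described as those of plasma components, and "All the adverse transfusion events will be recorded and managed by clinicians or investigators as per standard treatment".
- Expected adherence: SAP 4.2 says "No protocol deviation is expected and will adhere to the defined protocol of trial", and SAP 5.4 says "Withdrawal is not expected, follow up till 28 days in all enrolled patient".
- Per-protocol analysis, SAP 4.3.1: "There is no plan to do per-protocol (PP) population analysis as none will be allowed to switch to other treatment group".

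**The concern.** For a transfusion reaction, the numerator is set by exposure and the denominator by assignment. A Group A patient who dies, deteriorates or for any other reason gets no plasma cannot have such a reaction, but still counts among those at risk.

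The SAP expects full adherence but does not say how to handle a patient for whom that fails. Its ITT definition nevertheless allows for non-adherence. SAP 5.5 also treats the date of randomisation and the date transfusion starts as distinct, so there can be an interval between them in severely ill patients.

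At stake is the risk per transfused patient, which is the figure a clinician would want. No planned table is required to show it, and nothing requires the number of Group A patients not transfused to be reported. A reader of the planned tables might therefore be unable to work it out.

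**Working it through.** The SAP states no adverse-event rate, no share not transfused and no safety denominator, so it has no figure of its own to reproduce on this point.

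**Inputs**
- Plasma arm: 200 patients (SAP 1.3).
- f, the share of Group A never transfused: assumed, shown from 0% to 15%.
- r, the transfusion-reaction rate among transfused patients: assumed 5%.
- No Group B patient receives plasma (SAP 4.3.1 does not allow switching).

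**Transfusion-only events**

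Expected events are r × 200 × (1 - f), and the ITT denominator is 200. The reported rate is therefore r × (1 - f), and the relative understatement is f whatever r is.

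| f | Transfused | Reported rate if r = 5% |
|---|---|---|
| 0% | 200 | 5.0% |
| 2% | 196 | 4.9% |
| 5% | 190 | 4.75% |
| 10% | 180 | 4.5% |
| 15% | 170 | 4.25% |

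**If no such event is seen**

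The one-sided 95% upper bound is 1 - 0.05^(1/n). It is 1.49% on 200 patients, 1.56% on 190, 1.65% on 180 and 1.75% on 170. Using all 200 makes the bound slightly too reassuring when fewer were transfused.

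**All-cause events**

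Here the direction is not fixed. Assume f = 5%, a serious-event rate of 35% in transfused Group A patients, and 80% in those not transfused because of early death or deterioration. The ITT rate is 0.95 × 35% + 0.05 × 80% = 33.25% + 4% = 37.25%, which is above 35%. A between-arm excess caused by plasma is still diluted: an assumed 5 points becomes 0.95 × 5 = 4.75 points.

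**What regrouping by plasma received would do**

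Assume plasma has no effect, each arm of 200 has 10 early deaths (in Group A, before transfusion), and 35% of the other 190 have a serious event, which is 66.5 expected.
- ITT: (10 + 66.5) / 200 = 38.25% in both arms, correctly equal.
- As received, plasma: 66.5 / 190 = 35.0%.
- As received, no plasma: the 10 Group A deaths join Group B, giving (76.5 + 10) / 210 = 41.2%.

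This is a spurious advantage for plasma of about 6 points. The dilution in the table above at the same f (5%) is 5% - 4.75% = 0.25 points.

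**The case against.** The strongest reply is that the problem may never arise. The SAP expects no deviation, no switching and no withdrawal, and if that holds the bias is exactly zero. Section 5.2.2 excludes multi-organ failure, vasopressor need and a life expectancy under 24 hours, which makes death before transfusion less likely. Even at f of 5% or 10% the shift is 0.25 or 0.5 points, well inside sampling error: 10 events in 200 patients has an exact 95% interval of about 2.4% to 9.0%. The event counts do not depend on the analysis population, so all that is missing is the number transfused. ITT is also a defensible basis for all-cause events in an open-label trial.

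All of this stands as to size. It does not remove the point, because an expectation of full adherence is not a rule for when adherence fails, and the SAP does not ask for the missing count.

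Four stronger readings are tempting but unsupported:
- A reader might infer that transfusion risk will be understated. That follows only if f is above zero, and the SAP gives no f.
- A reader might infer that every safety rate is too low. For all-cause serious events the rate can move either way, as shown above.
- A reader might take 4.3.1 as the SAP's sole and mistaken reason for having no safety set. That sentence explains only why there is no per-protocol analysis, and 4.2 separately expects no deviation of any kind.
- A reader might conclude that all safety tables should be regrouped by plasma received. That would move deaths before transfusion into the no-plasma group and make plasma look safer than it is.

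**Conclusion.** The point holds in a narrow, conditional form. For transfusion reactions and events judged related to plasma, the rule in 4.4 gives a Group A rate of (1 - f) times the rate among transfused patients. That is no bias at f = 0, and 4.75% or 4.5% in place of an assumed 5% at f = 5% or 10%. Both f and the 5% are assumptions.

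The ITT table is sound as the between-arm comparison of all adverse events. The weakness is that it is the only basis for safety reporting. This is a minor matter and a cheap improvement.

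**What to change.** In SAP 4.4:
1. Keep the ITT table as the between-arm comparison of all adverse and serious adverse events.
2. Add one table of transfusion reactions and events judged related to plasma, with patients in whom any plasma transfusion was started as the denominator.
3. Report the number of Group A patients not transfused, and any Group B patients given plasma.
4. State that all-cause adverse and serious adverse events will not be regrouped by plasma received.

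The cost is a few lines of text and one extra table, built from the transfusion start dates used in 5.5 and the transfusion events recorded under 6.5. The added table is descriptive and not a randomised comparison, and should be labelled so.

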4.4.1 Serious adverse events

Serious Adverse Event (SAE) or Serious Adverse Reaction (SAR): any untoward medical

Occurrence or effect that at any dose of plasma transfusion:

- Results in death
 - Is life threatening
- refers to an event in which the patient will be at risk of death at the time of the event; it does not refer to an event which hypothetically might have caused death if it is more severe
- Requires hospitalization, or prolongation of existing in patients 'hospitalization
 - Results in persistent or significant disability or incapacity
 - Is a congenital anomaly or birth defect?

Medical judgment should be exercised in deciding whether an AE/AR is serious in other situations. Important AE/ARs that are not immediately life-threatening or do not result in death or hospitalization but may jeopardize the patient or may require intervention to prevent one of the other end points listed in the definition above, should also be considered serious. Information regarding serious toxicity, including Principal Investigator (PI) assessment, CTCAEv5.0 grade, will be summarized. Frequencies of all CTCAE events reported as SAEs will be produced and sorted by total frequency (high to low) and categorized using CTCAE system.

Section 5: Trial Population:

5.1 Screening data: All cases with possible COVID-19 will be screened for possible inclusion into the study based on inclusion and exclusion criteria.

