3.3 Sample size: The sample size was calculated by assuming median survival in SMT as 24 days, and convalescent plasma with 18 days giving a reduction of 25% of the median time; then with $\alpha=5\%$ and $\beta=20\%$, we need to enrol 190 participants in each treatment arm by survival analysis method. $(Z_{1-\alpha/2}+z_{\beta})^2/((\ln(\theta))^2)$ where $Z_{1-\alpha/2}=1.96$ and $z_{\beta}=0.84$, $\theta=\lambda_1=\log 2/24$ $\lambda_0=\log 2/18$. Hence, we enrolled 400 cases which were equally and randomly allocated into two arms

3.3 Framework: it will be a comparative trial with the motive of testing the efficacy of convalescent plasma in severe COVID 19 patients with standard medical trial.

3.4 Treatment allocation:

Patients will be randomized to one of two groups by block randomization:

- **Group A:** Convalescent Plasma plus standard medical treatment
- **Group B:** Standard medical treatment only.

3.5 Statistical interim analysis and stopping guidance:

3.5.1 Statistical interim analysis:

Since it is of short duration trial no interim analysis is proposed.

3.5.2 Stopping guidance: No stopping rule is proposed until or unless ethical or IRB or designated government authority may ask for stopping the trial.

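### The SAE definition is worded around plasma transfusion, which conflicts with safety reporting in both arms and makes SAE counts non-comparable if applied as written

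*SAP*

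**What the plan says.** SAP 4.4.1 opens with a combined definition, "Serious Adverse Event (SAE) or Serious Adverse Reaction (SAR): any untoward medical", and continues with the condition "Occurrence or effect that at any dose of plasma transfusion". The seriousness criteria follow as a list: death, threat to life, hospitalisation or its prolongation, disability, and congenital anomaly. The same section lets medical judgment class other important events or reactions as serious. It plans to tabulate the frequency of SAEs, sorted by total.

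SAP 3.4 assigns Group B to "Standard medical treatment only".

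SAP 4.4 states: "All safety reporting will be performed on the ITT population as per CTCAEv5.0 guidelines". SAP 4.3.2 defines that population: "This population includes all patients that will be randomized regardless of treatment adherence".

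SAP 6.1.2, item 7, lists "Incidence of adverse effects in both groups". SAP 2.2.2, item 11, gives the same outcome with a Day 28 time frame.

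SAP 6.5, in a paragraph on the risks of plasma components, says: "All the adverse transfusion events will be recorded".

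**The concern.** The population for safety is everyone randomised, but the definition of the event to be counted presupposes a treatment that only one arm receives. An ITT population settles who is in the denominator. It does not settle which events enter the numerator.

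The trial is open-label (SAP 3.1), so those recording events know who had plasma. Wording based on exposure then invites different ascertainment in the two arms. Two distortions are possible, depending on how staff read the text:

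- If every serious event after a transfusion counts and control events do not, the SAE table makes plasma look more harmful than it is.
- If only reactions attributed to the transfusion count, an excess over control of other serious events cannot be seen.

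The SAP does not settle which reading applies. Under either one the SAE table lacks a usable comparator.

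**Working it through.** The SAP states no SAE rate and no SAE figure, so there is nothing to reproduce. The check sets its sections against each other.

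1. **Who is covered by the definition.** The listed criteria in 4.4.1 sit under the plasma-dose condition. Group B gets no plasma (3.4). Read as written, a control patient's life-threatening event or prolonged hospitalisation does not meet the definition.

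2. **When it applies in the plasma arm.** SAP 5.5 measures time from either the start of transfusion or randomisation, so the two dates can differ. An event after randomisation but before transfusion occurs at no dose of plasma and is likewise outside the definition, although the ITT population includes the patient from randomisation.

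3. **Whether the medical-judgment text fills the gap.** It does not mention plasma, so it can be applied to control patients. It is, however, written for other situations: important events that are not immediately life-threatening and do not lead to death or hospitalisation. It therefore does not clearly bring in the gravest control events, which belong to the list under the plasma condition.

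4. **Whether 6.5 fills the gap.** Its recording sentence concerns transfusion events. It does not say that other events go unrecorded, but it does not provide for them either.

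5. **Which outputs depend on the definition.** The SAE frequency table in 4.4.1 does. The endpoint in 6.1.2, item 7, covers all adverse effects and does not use the SAE definition. Mortality at days 7 and 28 (6.1.2, item 5) is counted from randomisation in both arms. So are the ordinal scale (item 1) and mechanical ventilation at day 7 (item 4).

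6. **Possible size, by assumption only.** Let p be the true proportion of patients with an SAE, equal in both arms, with 200 per arm (SAP 1.3). If every plasma-arm SAE were counted and no control SAE were, the plasma count would be 200 × p and the control count 0:
   - p = 10%: 200 × 0.10 = 20 against 0
   - p = 20%: 200 × 0.20 = 40 against 0
   - p = 30%: 200 × 0.30 = 60 against 0

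   These are ceilings. Events before transfusion would lower the plasma count, and any control events that staff did record would raise the control count. If only transfusion reactions were counted, the plasma count would be lower still.

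**The case against.** The strongest case on the other side is that this is one badly worded clause in a plan that otherwise points to both arms. "All safety reporting will be performed on the ITT population" covers all randomised patients. The harm endpoint names both groups. The medical-judgment sentence is not limited to plasma recipients. Section 6.5 does not say that only transfusion events are recorded, and the collection of adverse events is commonly set out in the protocol, which is not shown. No between-arm SAE test is named, so no planned test fails. Deaths and respiratory worsening are captured in both arms by other endpoints.

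Most of this stands, and it limits the point. A reader might infer that a control patient cannot have an SAE at all, or that the planned comparison of harms is void. The SAP does not support either inference. The first takes one clause over the ITT rule and the medical-judgment text. The second overlooks that the both-groups endpoint is all adverse effects, not SAEs. Nor is a result such as 40 against 0 a prediction: it needs an assumed rate and complete one-sided counting.

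What the objection does not remove is the conflict itself. The SAP states a definition that does not fit its own safety population. That is not a detail left to the protocol. Non-fatal serious events other than those seen through the respiratory endpoints have no other stated route to a comparable count.

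**Conclusion.** The point holds as a conflict within the SAP. Section 4.4.1 merges events with reactions and words both around plasma, against 4.4, 4.3.2 and 6.1.2, and 6.5 leans the same way. Applied as written, SAEs in the control arm and SAEs before transfusion in the plasma arm would be under-counted, so SAE frequencies would not be comparable between arms.

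The effect is confined to SAE reporting. It does not touch the primary endpoint or the mortality comparisons, and it does not invalidate the endpoint on all adverse effects. The under-counting follows from the wording. Its extent rests on an SAE rate that the SAP does not give and on how literally staff apply the text; in practice they may record control events anyway. It is a moderate defect that should be corrected.

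**What to change.** - **4.4.1, SAE:** define it as any untoward medical occurrence from randomisation to Day 28, in either arm and whether or not plasma was given, that meets one of the listed seriousness criteria.
- **4.4.1, SAR:** define it separately, for transfused patients, and tabulate it separately.
- **6.5:** state that CTCAE v5.0 events are recorded in both arms over the same window, and keep the sentence on transfusion events as an addition.
- **SAE output:** report frequencies by arm, including the proportion of patients with at least one SAE and the difference between arms with a 95% confidence interval, the level already set in 4.1. The list sorted by total can stay.

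The cost is a change of wording and a little more event recording in the control arm, which the both-groups outcome with its Day 28 time frame already implies. Sample size, randomisation and the primary analysis are unaffected.
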